## **6.4 DOSE CHANGES**

No dose changes are necessary when taking alendronate. Participants should be instructed that if they miss a dose of study drug, they should take one tablet on the morning after they remember. They should not take two tablets on the same day but should return to taking one tablet once a week, as originally scheduled on their chosen day.

For participants requiring dental procedures, there are no data available to suggest whether discontinuation of bisphosphonate treatment reduces the risk of osteonecrosis of the jaw. Clinical judgement of the treating physician should guide the management plan of each participant based on individual benefit/risk assessment.

## **6.5 PARTICIPANT COMPLIANCE**

Study drug compliance will be monitored during the study with the assistance of:

- Pharmacy drug returns
- Investigator questioning
- Pill counts
- Self-reported treatment diary

Pill counts will be documented on a participant's CRF. Non-compliance is not in itself a reason to withdraw a patient from the trial. Participants who stop taking study drug should still be followed up as per study protocol unless another reason prevents this.

## **6.6 OVERDOSE**

Hypocalcaemia, hypophosphataemia and upper gastro-intestinal adverse events, such as upset stomach, heartburn, oesophagitis, gastritis, or ulcer, may result from oral overdosage.

No specific information is available on the treatment of overdosage with alendronate. If a participant overdoses (i.e. 2 or more tablets taken) calcium containing products (e.g. milk, antacids) should be given to bind alendronate. Owing to the risk of oesophageal irritation, vomiting should not be induced and the participant should remain fully upright.

## **6.7 OTHER MEDICATIONS**

### **6.7.1 Prohibited Medications**

Other bisphosphonates (zoledronate, risedronate, tiludronate, etidronate, pamidronate, non-study alendronate, etc.), drugs with antiresorptive activity (calcitonin, strontium ranelate), denosumab and PTH (Teriparatide/Forsteo) will be prohibited while a participant is on study treatment.

Participants who require to be treated with the above medications will be withdrawn from study treatment but should remain on study follow up schedule.

No other interactions with medicinal products of clinical significance are anticipated. Although specific interaction studies have not been performed, in clinical studies alendronate was used concomitantly with a wide range of commonly prescribed medicinal products without evidence of clinical adverse interactions.

Since NSAID use is associated with gastrointestinal irritation, caution should be used during concomitant use with alendronate.

### **6.7.2 Permitted Medications**

Excepting the prohibited medications listed in Section 6.7.1, participants are free to take their usual medication (including calcium and vitamin D) during the study.

Participants must wait at least 30 minutes after taking alendronate/placebo before taking any other oral medication as they may interfere with the absorption of the study drug.

Any regularly used medications that are being taken at the start of study or commenced while a participant is on study should be documented on the Concomitant Medication CRF.

## 7. STUDY ASSESSMENTS

### 7.1 SAFETY ASSESSMENTS

Prior to randomisation all participants require a baseline blood sample which must include creatinine, albumin, calcium and corrected/adjusted calcium. The results of the safety bloods are not required prior to randomisation, **but must be known and not show hypocalcaemia or poor renal function before the participant commences study therapy**. If the participant is randomised and then the safety blood sample shows that the participant is hypocalcaemic or has poor renal function (an eGFR of <35ml/min) then study medication should be stopped. These participants will be classed as post-randomisations exclusions and will continue follow-up as per protocol.

Pregnancy is contraindicated when on alendronic acid. As such, women of childbearing potential (WOCBP, defined as women who are **not** postmenopausal (12 months since last menses) or permanently sterilised) will require a negative urine pregnancy test prior to study inclusion. WOCBP will be required to use adequate contraception during the trial. Examples of adequate contraception include:

- Established use of oral, injected or implanted hormonal methods of contraception.
- Placement of an intrauterine device (IUD) or intrauterine system (IUS).
- Barrier methods of contraception: condom or occlusive cap (diaphragm or cervical/vault caps) **with** spermicidal foam/gel/film/cream/suppository.
- Male sterilisation.
- True abstinence. Periodic abstinence (e.g., calendar, ovulation, symptothermal, post-ovulation methods) and withdrawal are not acceptable methods of contraception.

The safety assessments outlined in Table 7–1 are considered a minimum requirement. Further safety assessments may be initiated at the treating physician's discretion if medically indicated.

Safety assessments will include the monitoring of adverse events and serious adverse events by the site investigator. For more details on adverse events please refer to Section 10.

### 7.2 STUDY ASSESSMENTS

Ideally, follow up visits for participants should be as close to the scheduled date as possible. It is recognised that in clinical practice this is not always feasible. As such, there is a window of +/-2 days for the visits up to and including the Week 8 visit and a window of +/- 7 days thereafter. For Weeks 2 to 8, a tolerance of +/-7 days is acceptable if the trial visit is being linked to a routine follow up visit or research clinic.

#### 7.2.1 Baseline Assessments

The following assessments and procedures should be performed at baseline. Please note that all baseline assessments must be completed in time to allow a participant to commence study therapy within 14 days of their initial fracture:

- Informed Consent
- Demographic data (including age, gender, smoking history and alcohol consumption)
- Assessment of eligibility (inclusion and exclusion criteria)
- Relevant medical history/current medical conditions
- Concomitant medication
- Biochemistry (minimum requirement is creatinine, albumin, calcium and corrected/adjusted calcium)
- Blood serum for biochemical markers (see Section 7.2.12)
- X-ray (performed at time of fracture)

- Pain assessment at fracture site using a 11 point NRS (**based on pain prior to fracture**)
- Analgesia use (**based on analgesia usage 24 hours before fracture**)
- DASH Questionnaire (**based on how the participant felt prior to fracture**)
- Urine pregnancy test (for women of child bearing potential)
- Genetic blood sample (optional – see section 7.2.11)

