#### Active range of movement

Active range of movement (AROM) will be measured at the wrist and distal radial-ulnar joints using a standard goniometer. The recording will be made in triplicate. The AROM of both the affected and unaffected hand will be measured.

The differences between the range of movement in each hand will be used to compare the two treatment groups.

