#### Grip strength

Grip strength will be measured using a JAMAR hand dynamometer using the guidelines for its use issued by the American Society for Surgery of the Hand. The grip strength of both the affected and unaffected hand will be measured.

The difference in grip strength between each hand will be used to compare the two treatment groups.

[figure not shown]

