### 4.3 EXCLUSION CRITERIA

1. Any of the following:
  - i) current or previous use of zoledronic acid
  - ii) current or previous use **within the last 2 years** of any other bisphosphonate.
  - iii) current or previous use **within the last 6 months** of strontium ranelate, calcitonin, denosumab, parathyroid hormone (PTH) or IV, IM and oral corticosteroids (inhaled corticosteroids such as asthma inhalers are acceptable).
2. Previous distal radial fracture on affected side.
3. Bilateral distal radial fracture.
4. Contraindications to alendronic acid, including but not limited to:
  - i) abnormalities of the oesophagus and other factors which delay oesophageal emptying such as stricture or achlasia
  - ii) inability to stand or sit upright for at least 30 minutes
  - iii) hypersensitivity to alendronate or any of its excipients
  - iv) known hypocalcaemia
  - v) known renal impairment
5. Women of childbearing potential not using adequate contraception.
6. Pregnancy (see Sections 7.1 and 11).
7. The distal radial fracture is due to other pathologies e.g. Paget's Disease of Bone, metastatic bone disease etc.

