### Notes for Table 7–1

---

- a All baseline assessments must be completed in time to allow a participant to commence study therapy within 14 days of their initial fracture.
- b Demographic information includes: age, gender, menopausal status, smoking history and alcohol consumption.
- c Minimum biochemistry requirement includes: creatinine, albumin, calcium and corrected/adjusted calcium.
- d X-rays must be performed +/- 2 days from scheduled visit date, except if it ties in with routine follow up/research clinic or at Week 26 X-ray where it can be +/- 7 days.
- e This X-ray refers to X-ray at time of fracture.
- f For women of childbearing potential
- g Discontinuation of study drug does not constitute withdrawal from trial. Unless there is another reason participants should continue to be followed up as per protocol.
- h Study drug administration must commence within the 14 days following initial trauma or within the 7 days following randomisation, whichever comes first.
- i Adverse events should be documented from date of randomisation to last study visit. Any adverse events ongoing at last study visit should be followed up until resolution or no longer medically indicated.
- j The optional genetic blood sample (9ml in EDTA tube) can be taken any time during the study. The participant must have given separate consent for this.
- k Telephone assessment will include questions about drug compliance and adverse event information. At week 24 patients will be reminded to stop taking study drug and bring all medication with them to their final study visit (week 26).

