## 9.2 PROPOSED ANALYSES

A detailed Statistical Analysis Plan will be developed and finalised prior to database lock and the trial being unblinded. This section sets out the basic principles which will be followed for the analysis.

The response of the primary outcome variable (fracture healing at 4 weeks) in the two randomised groups will be analysed using logistic regression with adjustment for the variables used in the randomisation algorithm (study site, gender, fracture status) and other variables known to influence fracture outcome (including age, the presence of comminution and ulnar variance at presentation on X-ray). The results will be presented as an adjusted odds ratio with the corresponding 95% confidence interval and p-value. In addition a simple unadjusted comparison of the two 4 week healing rates will be made, and the result presented as a difference in healing rates along with the corresponding 95% confidence interval. The primary analysis will be conducted on an intention-to-treat basis, but given the interest in the non-inferiority comparison the per-protocol analysis will be an important secondary analysis. A similar approach will be used for other categorical outcome variables. The identification of the per-protocol population will be agreed with the Trial Steering Committee (TSC) and finalised before the data are analysed.

The analysis of the time to fracture healing will not be straightforward as there is heavy interval censoring of these data (since the 'time of healing' cannot be observed directly, and rather all that is known is whether healing has occurred by Week 2, 4, 6 or 8 (or 26)). The analysis of interval censored data is an area of active statistical research and the precise approach to be used for this analysis will be chosen nearer the end of the trial. It is likely that a parametric survival analysis will be performed, using the same covariates as for the analysis of the fracture healing rates at 4 weeks. There are libraries of statistical code available which can be used with the package "R" to perform such analyses.

Analysis of covariance will be used to compare treatment effects on continuous variables such as the DASH score, with the corresponding baseline value and the covariates identified above being included in the models. The results will be presented as adjusted mean differences along with the corresponding 95% confidence intervals and p-values.

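### Grip and movement are compared hand against hand, but the protocol does not require hand dominance or earlier injury of the opposite wrist to be recorded, which costs some precision in these secondary endpoints

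*Protocol*

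**What the plan says.** **Endpoints.** Section 2.2.2 defines both physical measures as contrasts between a participant's two hands. For grip: "The difference in grip strength between each hand will be used to compare the two treatment groups". For movement: "The differences between the range of movement in each hand will be used to compare the two treatment groups". Sections 7.2.7 and 7.2.8 and Table 7–1 schedule both at weeks 8 and 26 only.

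**Baseline data.** Section 7.2.1 asks for "Demographic data (including age, gender, smoking history and alcohol consumption". Note b to Table 7–1 gives a slightly different list: "Demographic information includes: age, gender, menopausal status, smoking history and alcohol consumption". Neither mentions the dominant hand. The only item that might pick up an old injury of the other wrist is the general heading "Relevant medical history/current medical conditions".

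**Eligibility.** Section 4.3 excludes "Previous distal radial fracture on affected side" and, separately, "Bilateral distal radial fracture". Neither rules out someone whose opposite wrist was fractured in the past.

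**Analysis.** Section 5.5.1 stratifies by site, gender and displacement. Section 9.2 adjusts for those factors and for "other variables known to influence fracture outcome (including age, the presence of comminution and ulnar variance at presentation on X-ray". It carries the same covariates, with the outcome's own baseline value, into the analysis of covariance for continuous outcomes.

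**The concern.** The uninjured hand is the only within-person reference for grip and movement. The covariance model calls for a baseline value, but none exists for these two measures.

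If the dominant hand is naturally stronger by some amount d, the injured-minus-uninjured difference moves by +d when the dominant side is broken and by −d when the other side is broken. If dominance is not in the model, that movement stays in the residual. An earlier fracture of the reference wrist adds scatter in the same way, because the hand treated as unaffected is then not normal.

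The analysis plan can add a covariate, but only for data that were collected. What is collected at baseline is set in this protocol, so the gap is worth closing here. What is at stake is how sharply the trial can estimate two of its named secondary endpoints.

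**Working it through.** **1. The plan's own figure.** Section 9.1 claims at least 90% power for a 15-point difference in week 4 healing with 250 per arm at two-sided 5%, whatever the control rate. The formula is power = Φ{[0.15√n − 1.96√(2·p̄(1−p̄))] / √[p₁(1−p₁)+p₂(1−p₂)]}. The least favourable pair is 42.5% against 57.5%:

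- 0.15√250 = 2.372
- 1.96√0.5 = 1.386
- denominator = √0.48875 = 0.699
- (2.372 − 1.386)/0.699 = 1.410, so power is 92.1%

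The claim holds. With 200 per arm the lowest power is 85.4%, which also supports the statement of over 80% at 20% non-compliance. This point does not touch either figure. The protocol states no SD and no power for grip or movement.

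**2. Added variance from dominance.** Let p be the share of participants whose dominant side is injured, and d the dominance effect in residual SDs. A shift of +d or −d adds 4p(1−p)d² to the variance, which is d² when p = 0.5. Both p and d are assumptions.

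**3. Effect on power.** Take a true difference that the adjusted model would detect with 90% power at 250 per arm, so that the standardised effect is 1.960 + 1.282 = 3.242. Without adjustment, power = Φ(3.242/√(1+d²) − 1.960).

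| d (residual SDs) | Extra variance | Power without adjustment | Effective n per arm |
|---|---|---|---|
| 0.1 | 1% | 89.7% | 248 |
| 0.2 | 4% | 88.9% | 240 |
| 0.3 | 9% | 87.4% | 229 |
| 0.5 | 25% | 82.6% | 200 |

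Setting p to 0.3 or 0.4 changes little: at d = 0.5, power is 83.8% or 82.9%.

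**4. A central case in kilograms.** Assume a 2 kg dominance effect and a residual SD of 7 kg. Extra variance is 2²/7² = 4/49 = 8.2%. Then 3.242/√1.082 = 3.117 and 3.117 − 1.960 = 1.157, so power is about 87.6%. Effective n is 250/1.082, about 231 per arm.

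**5. Earlier injury of the reference wrist.** If a share q has such an injury and it shifts the between-hand difference by S residual SDs, the added variance is q(1−q)S². With q = 5% and S = 0.25 this is 0.05 × 0.95 × 0.0625 = 0.3% (power 89.9%). With q = 15% and S = 1 it is 0.15 × 0.85 × 1 = 12.75% (power 86.3%). Again q and S are assumed.

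**6. DASH.** DASH scores the whole person, so the plus-or-minus argument does not apply. If injury of the dominant side adds s points in half the participants, the added variance is (s/2)². With an assumed SD of 20, s = 4 gives 4/400 = 1%, and s = 10 gives 25/400 = 6.25%.

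**The case against.** **The items may be captured anyway.** A reader might infer that dominance is not recorded at all. The documents do not show that. The baseline list is worded as illustrative, and it differs from note b, which adds menopausal status. It also omits things the trial plainly needs, such as comminution and ulnar variance. An old wrist injury could be entered under medical history, and investigators must ask about earlier wrist fracture to apply the exclusion. Measurement guidelines for grip and movement sit in the site file, which is not at hand. This objection stands: the supportable statement is that the protocol does not require these items.

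**Covariates belong to the analysis plan.** Section 9.2 sets out principles only, its list of prognostic variables is open, and it already includes site, gender and age alongside the fracture features. Choosing one more covariate or sensitivity analysis is ordinary analysis-plan work. That also stands, and it leaves data capture as the substance of the point.

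**The loss can be repaired.** Dominance does not change and can be asked later, so the noise is not beyond removal.

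**The size is assumed.** No document gives a dominance effect or an SD for grip, movement or DASH. Nor do the documents establish that movement depends on dominance. The top of the range pairs a large effect with a small SD. Expressing the loss as extra participants would mislead, because 500 was set for week 4 healing and no secondary endpoint is powered.

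**It is not bias.** Randomisation balances dominance and old injuries on average, and the primary endpoint is a centrally read, blinded radiograph. Section 9.2 also promises very cautious reading of secondary p-values.

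**Conclusion.** The point holds as a modest, avoidable loss of precision in grip and movement. The protocol rests both on a between-hand difference with no baseline measurement, names dominance nowhere, and admits participants whose reference wrist was fractured before.

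For a dominance effect of 0.1 to 0.5 residual SD, the loss is 0.3 to 7.4 points of power from a 90% reference. In the central case it is about 2.4 points. These figures rest wholly on assumed values and show scale only.

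A reader might go further and infer biased functional comparisons, a weakened primary result or a need for more participants. The documents support none of these: allocation is randomised, the primary endpoint does not use the other hand, and its stated power reproduces. For DASH the case is weaker, and adjustment there is optional. Severity: minor.

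**What to change.** - **Section 7.2.1 and note b to Table 7–1:** add dominant hand, side of fracture, and any earlier fracture or lasting disorder of the opposite wrist or hand. For participants already enrolled, dominance can be collected retrospectively.
- **Section 9.2:** add whether the dominant side was injured (yes/no) as a covariate in the grip and movement models, and optionally in the DASH model.
- **Sensitivity analysis:** repeat the grip and movement comparisons without participants whose reference wrist was previously injured.

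The cost is a minor amendment to the case report form and one extra model term. No visit, procedure or participant is added.

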### 7.2.2 Radiological Assessment

Evaluation of fracture healing is the primary objective in this trial. Anterior-posterior (AP) and lateral radiographs of the wrist are required at **baseline** (when fracture occurs), **weeks 2, 4, 6, 8 and 26**.

Sites are required to send radiographs to the coordinating centre for central analysis. Radiographs should be anonymised and only identified by participant trial number, initials, date of birth and date of radiograph. For guidance on sending radiographs for central analysis please refer to the Investigator Site File (ISF).

### 7.2.3 Pain Assessment

Evaluation of pain at fracture site should be performed using an 11-point NRS. This scale ranges from 0 (no pain at all) to 10 (worst pain possible).

Pain assessment using the NRS should be done at **baseline** (this should be based on the participant's pain levels the day before fracture), **weeks 2, 4, 6, 8 and 26**.

### 7.2.4 Analgesic use

Assessment of analgesic use will be noted by documenting any analgesia taken by the participant in the last 24 hours prior to questioning, except at baseline when the analgesia used in the 24 hours prior to fracture should be documented.

Evaluation of a participant's analgesic use should be performed at **baseline, weeks 2, 4, 6, 8 and 26**.

### 7.2.5 DASH Questionnaire

The DASH Outcome Measure is a 30-item, self-report questionnaire designed to measure physical function and symptoms in patients with any or several musculoskeletal disorders of the upper limb.

Participants will be asked to complete the DASH at **baseline, weeks 2, 4, 6, 8 and 26**. Study staff will check to ensure that all questions have been answered prior to the participant leaving the study visit.

### 7.2.6 CRPS-I Assessment

CRPS-I will be assessed using an assessment tool based on the International Association for the Study of Pain's (IASP) Budapest Criteria.

CRPS-I assessment will be performed at **week 6 and week 26**.

### 7.2.7 Active Range of Movement

AROM will be assessed in participants' affected and unaffected wrist and distal radio-ulnar joint using a goniometer. Range of movement will be measured for flexion/extension, radial/ulnar deviation and supination/pronation. Each individual movement will be performed and measured 3 times. Guidelines for measuring AROM are available in the ISF.

AROM will be performed at **week 8 and week 26**.

### 7.2.8 Grip Strength

Grip strength will be measured using a JAMAR hand dynamometer in both the affected and unaffected hand. Grip strength will be performed and measured 3 times at each required time point. Guidelines for measuring grip strength are available in the ISF.

Grip strength will be performed at **week 8 and week 26**.

### **7.2.9 Study drug compliance**

Compliance will be assessed by the investigator and/or study personnel at each visit. A variety of methods will be used to ensure compliance. This information should be captured in the source document.

See Section 6.5 for further details on study drug compliance.

